#### **4.2.2 Adverse Events**

An adverse event (AE) is any undesirable physical, psychological or behavioral effect experienced by a patient during the study, in conjunction with the use of the study medication, whether or not product-related. This includes any untoward signs or symptoms experienced by the patient from the time of signing of the informed consent until completion of the study.

AEs may include, but are not limited to:

- Subjective or objective symptoms spontaneously offered by the patient and/or observed by the Investigator or medical staff.
- Findings at physical examinations.

- Laboratory abnormalities of clinical significance.

HAE attacks (not treated with study medication) will be reported separately from other AEs.

AE data was collected from the time that informed consent was given, for the duration of the trial.

Missing AE data will be handled according to the rules specified in Section 5.5.2.2.

#### **4.2.2.1 Adverse Event Definitions**

A treatment-emergent adverse event (TEAE) is defined as an AE that occurred or increased in severity within 97 days of a dose of study medication. If there are partial or missing dates for when the AE started then it will be assumed that the AE was treatment emergent unless it can be determined from the partial start date or stop date that the AE definitely started before the first dose of study medication, or more than 97 days after the patient last received study medication. Tables will include only TEAEs, but all AEs will be listed.

Serious adverse events (SAEs) reported from the time of informed consent until the last follow-up visit (Day 90) after the last dose of study medication will be recorded as part of the study. SAEs will be any AE where the question 'Does the adverse event meet the criteria of serious?' has been answered as 'Yes'.

A treatment-emergent serious adverse event (TESAE) is defined in exactly the same manner as a TEAE, with the exception that the AE in question must be classified as an SAE.

Each AE will be assigned to an attack based on the start date. If the AE starts after study medication was received for Attack N but prior to study medication being received for Attack N+1 then the AE will be assigned to Attack N. If it is not possible to ascertain from the partial date during which attack the AE occurred then the AE will be assigned to the last possible attack based on the partial date.

The time from previous administration of study drug to onset of an AE will be calculated for all TEAEs as follows:

Date/Time of onset of AE – Date/Time of the start of previous administration of study drug.

An AE will be classified as related to study medication if the relationship to study medication was recorded (on the 'Study Adverse Events' CRF page,) as, 'Possible', 'Probable', 'Definite'. An AE will be classified as unrelated to study medication if the relationship to study medication was recorded as 'Unrelated'.

An AE leading to study discontinuation will be defined as an AE where 'Action taken discontinued study drug' is selected on the Adverse Events CRF page and/or '(Serious) Adverse Event experience' is selected as reason for end of study on the End of Study CRF page.

An AE leading to death will be any AE where the outcome is marked as "4 (Death)".

Adverse Events of Special Interest (AEOSI) are AEs that do not meet any criteria for an SAE but are nonetheless of particular interest in the context of this study, as listed below:

- Type I hypersensitivity reaction due to pre-existing IgE antibodies against rabbit antigens.

- Type I hypersensitivity reaction due to cross reaction with IgE antibodies against cow milk antigens.
- Type I hypersensitivity reaction due to the formation of IgE antibodies against rabbit antigens.
- Type III hypersensitivity reaction due to the formation of antibodies against Ruconest.
- Induction of acquired angioedema due to the formation of anti-C1 inhibitor antibodies.
- Thromboembolic complications.

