11.1.2 Adverse Event Intensity

The Investigator will be required to assess the intensity of the adverse drug/biologic experience using the following categories to quantify intensity.

- **Mild:** events require minimal or no treatment and do not interfere with the patient's daily activities.
- **Moderate:** events result in a low level of inconvenience or concern with the therapeutic measures. Moderate events may cause some interference with functioning.
- **Severe:** events interrupt a patient's usual daily activity and may require systemic drug therapy or other treatment. Severe events are usually incapacitating.
- **Life threatening:** Potentially life-threatening or disabling. High-risk medical interventions.
- **Fatal:** patient died

Changes in the severity of an AE will be documented to allow an assessment of the duration of the event at each level of intensity to be performed. Adverse events characterized as intermittent require documentation of onset and duration of each episode.

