#### **4.2.2.2 Coding of Adverse Event Terms**

The AE term (Investigator term) will be assigned to the lowest level term (LLT), and a preferred term (PT) will be classified by a system organ class (SOC) according to the Medical Dictionary for Regulatory Activities (MedDRA) thesaurus, Version 20.

Although there can be multiple SOCs for a PT, each PT will be linked with one SOC, namely the primary SOC which is automatically assigned by MedDRA.

The following coding data will be presented:

- LLT
- PT
- SOC

Coding of AEs will be provided by data management at PSR in a coding spreadsheet alongside the coding of CMs and MH. The AE coding data will be merged onto the raw AE data by Subject ID and AE number. The final version of this spreadsheet will be provided prior to database lock.

In the event that no coding information is available for a specific AE, the AE will be presented as an 'Uncodable Event' in all summary tables.

AEs will be reported on a per-patient basis. On a per-patient basis this means that even if a patient reported the same event repeatedly (i.e., events mapped to the same PT) during the study period, the event will be counted only once. In the latter case the event will be assigned the worst severity and the strongest relationship to the study medication. The earliest date will be regarded as start date of the event and the latest date/time will be regarded as stop date of the event within the assigned study period.

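### SAP 4.2.2.1 counts an AE that worsens after a dose as treatment-emergent but places and times it by its start, so by-attack and time-window tables can show it under an earlier attack or not at all

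*SAP*

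**What the plan says.** SAP 4.2.2.1 gives two routes to treatment emergence, new onset and worsening, by counting "an AE that occurred or increased in severity within 97 days of a dose of study medication".

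The other rules in that section look only at when the AE began:

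- **Attack.** "Each AE will be assigned to an attack based on the start date". The condition for Attack N is "If the AE starts after study medication was received for Attack N but prior to study medication being received for Attack N+1". There is no rule for a start before the first dose.
- **Time from administration**, required for all TEAEs: "Date/Time of onset of AE – Date/Time of the start of previous administration of study drug".
- **Partial dates.** The presumption of treatment emergence is lifted in only two cases: where "it can be determined from the partial start date or stop date that the AE definitely started before the first dose of study medication", and where onset came more than 97 days after the last dose. Worsening is not considered.

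SAP 6.8.2 presents the AE tables by attack, with an extra column that ignores attack number. Two tables count TEAEs that begin within 24 hours or 28 days of the end of the infusion. All AEs are listed.

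Protocol 12.3.3 defines TEAEs by onset only, between the start of treatment and 97 days after treatment for any treated attack. It lists AEs that began before the first treatment as baseline events. SAP 7.1, which covers departures from the protocol's analyses, mentions only the reduced set of PK parameters.

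**The concern.** Start-date assignment fits the protocol's onset-only definition. Once worsening also qualifies an AE, the date that makes it treatment-emergent can differ from the date that decides its attack, its time from dose and its entry in the time-window tables. The SAP does not connect the two.

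This matters because safety and tolerability are the primary objective. Children may be treated for up to 10 attacks, as little as 24 hours apart (Protocol section 6), and AEs are collected from consent onwards (Protocol 11.1.1). An AE can therefore be under way when a dose is given. The by-attack tables, including maximum severity, and the 24-hour table are where a reader looks for poor tolerance of repeat doses or acute effects. An AE that worsens soon after a later dose would not be shown against that dose.

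**Working it through.** The plan states no figure to reproduce here, apart from the window: Day 90 plus the 7-day visit allowance gives 90 + 7 = 97 days, which is not in dispute. The check applies the written rules to hypothetical records.

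**Assumptions.** Doses on day 0 (Attack 1) and day 40 (Attack 2). Each worsened AE stays one record with its original start date.

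**Rules** (d = day of a dose):

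- TEAE, SAP: 0 ≤ onset − d ≤ 97 or 0 ≤ worsening − d ≤ 97, for any dose.
- TEAE, protocol: 0 ≤ onset − d ≤ 97, for any dose.
- Attack, SAP: the latest attack whose dose came before onset.
- Time, SAP: onset minus the latest dose before onset.

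**As written:**

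| Record | Onset | Worsens | TEAE, protocol | TEAE, SAP | Attack | Time | 24-hour table |
|---|---|---|---|---|---|---|---|
| A | −3 | 0.5 | no | yes (0.5 − 0 = 0.5) | none | none | no |
| B | 30 | 40.5 | yes (30 − 0 = 30) | yes | 1 | 30 − 0 = 30 days | no |
| C | −3 | 40.5 | no | yes (40.5 − 40 = 0.5) | none | none | no |
| D (control) | 41 | – | yes | yes | 2 | 41 − 40 = 1 day | yes |

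**With the worsening placed by its own date:**

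| Record | Attack | Time | 24-hour table |
|---|---|---|---|
| A | 1 | 0.5 − 0 = 0.5 day | yes |
| B | 2 | 40.5 − 40 = 0.5 day | yes |
| C | 2 | 40.5 − 40 = 0.5 day | yes |
| D | 2 | 1 day (unchanged) | yes |

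A and C also miss the 28-day table, because they began before any dose. B misses it because 30 > 28. With onset on day 10 it would enter that table, but under Attack 1, and it would still miss the 24-hour table.

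Suppose B is mild at onset and severe after the Attack 2 dose. The maximum-severity table then shows one severe event under Attack 1 and none under Attack 2. The overall column shows one severe event whichever date is used.

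Under the protocol's definition A and C are baseline events and B belongs to Attack 1 by onset. A TEAE without an attack therefore arises only from the SAP's added criterion.

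**The case against.** **Recording may remove the problem.** The misplacement needs a worsened AE to remain one record. Protocol 11.1.1 says that findings present before Ruconest are not AEs unless they recur or worsen to a clinically significant degree. On that reading the exacerbation could be the AE, with its own post-dose start, and A would fall under Attack 1. Neither document settles this, so the point is conditional. The indications favour one record: Protocol 11.1.2 says "Changes in the severity of an AE will be documented to allow an assessment of the duration of the event at each level of intensity", which describes one event with several grades, and Protocol 10.2.4.2 and 10.2.4.3 ask sites to record changes to ongoing AEs. If each worsening opened a new record, the SAP's worsening clause would be unnecessary.

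**Nothing is lost overall.** This stands for total TEAE incidence, relatedness and maximum severity, which the overall column preserves, and for the listings. It does not hold for the 24-hour table, where A, B and C are absent from every column.

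**The time-window tables are titled by commencement.** They do what they say. Even so, a TEAE that qualifies only by worsening can be left out of the tables meant to show events soon after a dose.

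**B really did begin under Attack 1.** This is correct. It is a TEAE by onset, so its entry under Attack 1 is not false. What is missing is any trace of the worsening under Attack 2.

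**A stronger reading of the same-term rule.** SAP 4.2.2.2 says that for repeated reports of a term "the event will be assigned the worst severity and the strongest relationship to the study medication. The earliest date will be regarded as start date". A reader might infer that a term recurring more severely after a later dose is pulled back to the earlier attack. The documents do not support this. The date rule is limited to the assigned study period, a recurrence has its own start date, and SAP 6.8.2 merges an AE seen in several attacks only in the overall column.

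**Conclusion.** The inconsistency is in the text, and its effect is limited. If a worsened AE keeps one record and its first start date:

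- an AE that began before the first dose and worsened after any dose is a TEAE with no attack, no time from administration and no entry in the 24-hour or 28-day table;
- an AE that began more than 24 hours after the Attack 1 dose and worsened after the Attack 2 dose is shown, with its worst grade, only under Attack 1, and is absent from the 24-hour table.

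The by-attack and time-window tables are affected. The listings, and the overall column of tables without a time window, are not. A reader might conclude that every worsening TEAE is misplaced or that events drop out of the safety report; the documents support neither.

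The documents give no frequency. For scale only, one child in a column of 20 is 1/20 = 5 percentage points, and more in a smaller later-attack column; this is not an estimate of bias. The study is descriptive and tests no hypothesis, so no inference changes. The point is worth correcting because it concerns the primary objective and the correction is cheap.

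**What to change.** Choose one of two routes.

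1. **Keep worsening.** Add to SAP 4.2.2.1: any increase in severity after a later dose is assigned to the attack whose dose most recently preceded the increase. The date and time of the increase are used for time from administration and for the 24-hour and 28-day tables. The original onset, and the grade before the increase, stay with the earlier attack, if any. This applies whether or not the AE was already a TEAE by onset. That last sentence is needed because a rule limited to AEs that qualify only by worsening would leave record B where it is.
2. **Return to the protocol's onset-only definition**, which already agrees with start-date assignment.

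Either choice belongs in SAP 7.1. The SOP deviation form attached to the SAP says that the analysis is finalised, so the practical route is the one in SAP 7.5: describe and justify the choice in the CSR, and rerun the affected tables or identify the affected AEs. SAP 4.2.2.2 needs no change.

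The cost is a few sentences and a small change to the AE derivation. The protocol already requires severity changes to be documented. If the CRF holds only the date of a change and not its time, the 24-hour table also needs a stated convention.

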10.5 Follow-up of patients withdrawn from treatment

When a patient withdraws from the study a full medical examination (including blood sampling for routine safety and immunology analyses) will be performed and follow-up visits Day 28 and Day 90 will be completed whenever possible. In case of treatment discontinuation because of severe or serious adverse events additional blood sampling for hematological, blood chemistry and urine laboratory tests or other special examinations may be performed. As described, such patients will continue to be followed as specified by the protocol unless they refuse such follow-up. Patients

who are withdrawn from treatment due to an AE will be monitored closely until resolution of the event or stabilization, at the discretion of the investigator.

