11.1.4 Serious Adverse Events

Serious adverse events (SAEs) will be reportable from the time the patient signs the ICF through the last follow-up visit (Day 90 after the last treatment. Adverse events and serious adverse

Safety of Ruconest in 2-13 year old HAE patients

events will not be collected in patients who sign the informed consent but are considered a screen failure. Investigators need to complete the Screen Failure CRF which will identify the reason for the screen failure. Patients terminated prematurely from the study due to withdrawal of consent will continue to be followed as specified by the protocol unless they refuse such follow-up. Patients who are withdrawn from treatment due to an adverse event will be monitored closely until resolution of the event or stabilization, at the discretion of the investigator.

An SAE is any AE that results in any of the following outcomes:

- Death
- Life-threatening experience
- Required or prolonged inpatient hospitalization
- Persistent or significant disability/incapacity
- Congenital anomaly
- Important medical events that, based upon appropriate medical judgment, may jeopardize the patient and may require medical or surgical intervention to prevent 1 of the outcomes listed above.

Life-threatening experience. Any adverse experience that places the patient, in the view of the reporter, at immediate risk of death from the adverse experience as it occurred, i.e., does not include an adverse experience that had it occurred in a more severe form, might have caused death.

Required or prolonged inpatient hospitalization. The adverse experience resulted in an initial inpatient hospitalization or prolonged an existing hospitalization of the patient. If a patient is hospitalized as part of the clinical use of the product, a period of normal hospitalization will be outlined in the protocol or by the judgment of the Investigator. Hospitalizations longer than this period will be prolonged hospitalizations.

Persistent or significant disability/incapacity. An adverse experience that resulted in a substantial disruption of a person's ability to conduct normal life functions.

Congenital Anomaly. The exposure of the patient to the drug or biologic during pregnancy that is judged to have resulted in the congenital anomaly/birth defect.

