### 6.8.2 Adverse Events

AEs will be recorded throughout the study. These will be coded using the MedDRA dictionary, version 18.0 or later. Tables will only summarize TEAEs; all AEs will be listed.

TEAEs will be summarized using absolute counts (n) and percentages (%). Summaries will be presented by SOC and PT. Results will be sorted by decreasing frequency of the SOC and PT within the SOC.

AE tables will be presented by attack for the Safety Analysis Set. A separate column will be included summarizing AEs reported regardless of attack number. For the overall column, percentages will be presented out of the total number of patients in the Safety Analysis Set and counting will be by patient, so if a patient has the same AE in more than one attack this will only be counted once in the overall column.

The following tables will be produced:

- Overall summary of Adverse Events
- Incidence of Treatment-Emergent Adverse Events
- Incidence of Related Treatment-Emergent Adverse Events
- Incidence of Treatment-Emergent Adverse Events Commencing Within 24 Hours of the Completion of the Infusion of Study Drug Administration
- Incidence of Treatment-Emergent Adverse Events Commencing Within 28 Days of the Completion of the Infusion of Study Drug Administration
- Incidence of Treatment-Emergent Adverse Events by Strongest Relationship (Investigator's Judgment)
- Incidence of Treatment-Emergent Adverse Events by Maximum Severity (Investigator's Judgment)
- Incidence of Treatment-Emergent Serious Adverse Events
- Incidence of Treatment-Emergent Adverse Events Leading to Study Discontinuation
- Incidence of Treatment-Emergent Adverse Events of Special Interest

The Summary of Adverse Events table will be presented by attack and will show the following:

- Number (%) of Deaths
- Number (%) of Treatment-Emergent Deaths
- Number (%) of Subjects With At Least One SAE
- Number (%) of Subjects With At Least One TESAE
- Number (%) of Subjects Who Prematurely Discontinued the Study Due to a TEAE
- Number (%) of Subjects With At Least One TEAE
- Number (%) of Subjects With At Least One Related TEAE
- Number (%) of Subjects Without Any TEAEs

All AEs will be listed. Listings will include CRF collected data, coded terms (primary SOC and PT) and a flag for treatment emergence. The time from last administration of study drug to onset of an AE (hours) will be listed for TEAEs. Separate listings will be produced for any SAEs and any AEs leading to study discontinuation.

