Table 14.2.2.1.2	Functional C1INH (% of Normal) Cmax and AUC(0-3) Parameters	PK/PD Analysis Set	Unique
Table 14.2.2.2	C4 Concentrations Over Time	PK/PD	Unique

Table Number	Title	Analysis Set	Repeat
		Concentration Set	
Table 14.3.1.1	Summary of Adverse Events	Safety	Unique
Table 14.3.1.2.1	Incidence of Treatment-Emergent Adverse Events	Safety	Unique
Table 14.3.1.2.2	Incidence of Related Treatment-Emergent Adverse Events	Safety	Repeat of 14.3.1.2.1
Table 14.3.1.2.3	Incidence of Treatment-Emergent Adverse Events Commencing Within 24 Hours of the Completion of the Infusion of Study Drug Administration	Safety	Repeat of 14.3.1.2.1
Table 14.3.1.2.4	Incidence of Treatment-Emergent Adverse Events Commencing Within 28 Days of the Completion of the Infusion of Study Drug Administration	Safety	Repeat of 14.3.1.2.1
Table 14.3.1.2.5	Incidence of Treatment-Emergent Adverse Events by Strongest Relationship (Investigator's Judgment)	Safety	Unique
Table 14.3.1.2.6	Incidence of Treatment-Emergent Adverse Events by Maximum Severity (Investigator's Judgment)	Safety	Unique
Table 14.3.2.1	Incidence of Treatment-Emergent Serious Adverse Events	Safety	Unique
Table 14.3.2.2	Incidence of Treatment-Emergent Adverse Events Leading to Study Discontinuation	Safety	Repeat of 14.3.2.1
Table 14.3.2.3	Incidence of Treatment-Emergent Adverse Events of Special Interest	Safety	Repeat of 14.3.2.1
Table 14.3.4.1.1	Summary of Quantitative Laboratory Parameters	Safety	Unique
Table 14.3.4.1.2	Summary of Change in Quantitative Laboratory Parameters from Presentation of Attack to Day 28	Safety	Repeat of 14.3.4.1.1
Table 14.3.4.1.3	Summary of Quantitative Laboratory Parameter Classifications Based on Laboratory Reference Ranges	Safety	Unique
Table 14.3.4.1.4	Change in Status of Hematology Laboratory Parameters Based on Laboratory Reference Ranges from Presentation of Attack to Day 28	Safety	Unique
Table 14.3.4.1.5	Change in Status of Biochemistry Laboratory Parameters Based on Laboratory Reference Ranges from Presentation of Attack to Day 28	Safety	Unique
Table 14.3.4.1.6	Incidence of Clinically Significant Quantitative Laboratory Parameters	Safety	Unique
Table 14.3.4.1.7	Change in Status of Quantitative Laboratory Parameters According to Clinical Significance from Presentation of Attack to Day 28	Safety	Unique
Table 14.3.4.2.1	Summary of Exposure to Study Medication	Safety	Unique
Table 14.3.4.2.2	Total exposure to rhC1INH	Safety	Unique

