**Quantitate**  
The Clinical Data Experts

Table Number	Title	Analysis Set	Repeat
Listing 16.2.1	Listing of Patient Disposition	All Patients	Unique
Listing 16.2.2	Listing of Protocol Violations	All Patients	Unique
Listing 16.2.3	Patients Excluded from the Efficacy Analysis	All Patients	Unique
Listing 16.2.4.1	Listing of Demographics and Baseline Patient Characteristics	All Patients	Unique
Listing 16.2.4.2	Listing of Medical History	All Patients	Unique
Listing 16.2.4.3	Listing of Relevant HAE history	All Patients	Unique
Listing 16.2.4.4	Listing of Relevant HAE attack history	All Patients	Unique
Listing 16.2.4.5	Listing of Concomitant Medications	All Patients	Unique
Listing 16.2.5.1	Listing of Study Medication Administration	All Patients	Unique
Listing 16.2.6.1.1	Listing of VAS and change from Baseline in VAS	All Patients	Unique
Listing 16.2.6.1.2	Listing of TEQ	All Patients	Unique
Listing 16.2.6.1.3	Listing of Investigator Symptom Score (IS)	All Patients	Unique
Listing 16.2.6.1.4	Listing of time to event endpoints and therapeutic failure	All Patients	Unique
Listing 16.2.6.2.1	Listing of PK/PD concentrations	All Patients	Unique
Listing 16.2.7.1	Listing of Adverse Events	All Patients	Unique
Listing 16.2.7.2	Listing of Serious Adverse Events	All Patients	Unique
Listing 16.2.7.3	Listing of Adverse Events Leading to Discontinuation from Study	All Patients	Unique
Listing 16.2.8.1	Listing of Clinical Laboratory Parameters	All Patients	Unique
Listing 16.2.8.2	Listing of ECG Parameters	All Patients	Unique
Listing 16.2.8.3	Listing of Vital Signs	All Patients	Unique
Listing 16.2.8.4	Listing of Physical Examination	All Patients	Unique
Listing 16.2.8.5	Listing of HAE Attacks	All Patients	Unique
Listing 16.2.8.6.1	Initial ELISA Immunology Results	All Patients	Unique
Listing 16.2.8.6.2	Neutralizing and Displacement Assay Immunology Results	All Patients	Unique
Listing 16.2.8.6.3	Initial ELISA Immunology Results – Patients with a Confirmed Positive Result	All Patients	Unique
Listing 16.2.8.6.4	Neutralizing and Displacement Assay Immunology Results – Patients with a Confirmed Positive Result	All Patients	Unique
Listing 16.2.8.7	Listing of Diagnostic Parameters	All Patients	Unique
Figure 14.2.1.1.1	Kaplan Meier Plot of Time to Beginning of Relief for First Attack (VAS)	ITT	Unique
Figure 14.2.1.1.2	Kaplan Meier Plot of Time to Beginning of Relief for Last Attack (VAS)	ITT	Repeat of Figure 14.2.1.1.1

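### The SAP labels stopping study drug for an adverse event as discontinuing the study, so its study-discontinuation summaries can count children who never left

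*SAP*

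**What the plan says.** SAP section 4.2.2.1 gives the only definition of discontinuation due to an adverse event (AE): "An AE leading to study discontinuation will be defined as an AE where 'Action taken discontinued study drug' is selected" on the AE page of the CRF, "and/or '(Serious) Adverse Event experience' is selected as reason for end of study on the End of Study CRF page". Because the two criteria are joined by and/or, either is sufficient.

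Three planned outputs use this concept, and all are worded as leaving the study:

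- the row "Number (%) of Subjects Who Prematurely Discontinued the Study Due to a TEAE" in the AE summary (SAP 6.8.2, Table 14.3.1.1);
- Table 14.3.2.2, "Incidence of Treatment-Emergent Adverse Events Leading to Study Discontinuation";
- Listing 16.2.7.3, "Listing of Adverse Events Leading to Discontinuation from Study".

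No AE table for discontinuation of study drug is planned alongside them.

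Protocol 10.3 names two separate acts: a patient may withdraw from the study, and the investigator may stop study treatment. For treatment stopped because of severe or serious AEs, protocol 10.5 says that "such patients will continue to be followed as specified by the protocol unless they refuse such follow-up". Protocol 11.1.4 adds: "Patients who are withdrawn from treatment due to an adverse event will be monitored closely until resolution of the event or stabilization". The analysis planned in protocol 12.3.3 is a count of patients whose treatment-emergent AEs (TEAEs) caused premature discontinuation, without saying whether of drug or of study.

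**The concern.** A child whose treatment is stopped for an AE, but who stays in follow-up, meets the first criterion and is reported as having left the study. Up to 10 attacks per child may be treated, with visits after each treatment and yearly, so stopping treatment while remaining under observation is a realistic course.

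Safety and tolerability are the primary objective, and SAP 5.2 plans no hypothesis test, so the descriptive tables carry the conclusion. Study withdrawal due to an AE and treatment stopped due to an AE answer different questions. Pooled under the label of the first, the summary row gives neither rate. It can also disagree with the disposition tables of the same report, which take study withdrawal and its reason directly (SAP 4.3.4).

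A secondary concern is the other criterion. It is a reason for ending the study, and the SAP states no rule for tying it to one particular AE.

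**Working it through.** **Plan's own figure.** There is none to reproduce: the SAP states no expected discontinuation rate and no formal sample size.

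**The definition against the protocol**

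| Child's course | Protocol status | SAP 4.2.2.1 |
|---|---|---|
| Drug stopped for a severe or serious AE, follow-up not refused | Treatment stopped, still followed (10.5) | Flagged by the drug action alone |
| Leaves the study, AE given as End of Study reason | Withdrawn from the study | Flagged by the End of Study reason |

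The first line is the mislabelled case. In the second the label is right, but the AE responsible is not identified by any stated rule.

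**Size of the first effect.** Input: at least 20 treated children (protocol 7.5, SAP 2.3). The overall column counts patients, with the Safety Analysis Set as denominator (SAP 6.8.2). Each child who stops drug but stays adds 100/N percentage points, which at N = 20 is 100/20 = 5.0; with more children treated it is smaller. Exact (Clopper-Pearson) 95% intervals at N = 20:

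- 0/20 = 0%, interval 0 to 16.8%
- 1/20 = 5.0%, interval 0.1 to 24.9%
- 2/20 = 10.0%, interval 1.2 to 31.7%

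**Both effects in an invented example (not trial data).** N = 20. Child A stops drug for one AE and stays in follow-up. Child B ends the study for an AE and has four TEAEs with different preferred terms, two in attack 1 and two in attack 2. One of those in attack 2 caused both the drug stop and the exit.

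| Rule | Subjects | Preferred-term entries | Subjects, attack 1 / attack 2 |
|---|---|---|---|
| SAP, End of Study reason applied to all of B's TEAEs | 2/20 = 10.0% | 1 + 4 = 5 | 2 / 1 |
| SAP, End of Study reason applied only to the causal AE | 2/20 = 10.0% | 1 + 1 = 2 | 1 / 1 |
| Study withdrawal, AE identified | 1/20 = 5.0% | 1 | 0 / 1 |
| Drug discontinuation, AE identified | 2/20 = 10.0% | 2 | 1 / 1 |

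The first two lines share the same subject count, and both exceed true study withdrawal by child A. The excess in the overall row therefore comes entirely from counting a drug stop as a study exit. The missing link to a particular AE changes only the preferred-term entries (5 against 2) and the attack 1 column (2 against 1).

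**The case against.** The strongest reply has four parts.

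**The protocol blurs the two ideas itself.** Its analysis section does not say what is discontinued, and its subject stopping rule (10.6) says only that the subject is withdrawn. For a patient who withdraws from the study, 10.5 still asks that "follow-up visits Day 28 and Day 90 will be completed whenever possible". A composite of drug stop and study exit is thus a permissible reading of the planned analysis. This stands in part: completing Day 90 cannot be used to decide who left, and no output promised by the protocol is lost. It does not excuse labelling the composite as study discontinuation, since 10.3 and 10.5 do treat the two acts differently.

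**The End of Study criterion has a natural reading.** It most plausibly means the AE that was the reason. A reader might infer that every TEAE of a child who left is flagged and that the headline figure is inflated accordingly. The documents do not support this. The CRF is not among them and its End of Study page may name the AE; and the child did leave for an AE and is counted once in the overall column. What remains is that the linking rule is unstated.

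**Nothing shows that such cases exist.** Protocol 9.3 reports no AE leading to discontinuation of study medication in Study C1 1207 or the C1 1304-01 extension, and none leading to premature study discontinuation among the adolescents. Any error would overstate study discontinuation, which is cautious for a safety objective. This stands as a limit on size; but an inclusive count under the wrong name still does not report the quantity named.

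**Much can be recovered.** Disposition output gives the date and reason of study withdrawal, and the AE listing carries the CRF data collected. With about 20 children a careful reader could probably separate the cases. That helps a reader of the listings, but leaves the summary row and table mislabelled.

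**Conclusion.** The point holds as a fault of definition and labelling. Followed as written, SAP 4.2.2.1 lets the study-discontinuation row, Table 14.3.2.2 and Listing 16.2.7.3 count children whose treatment was stopped but who remained in the study, and drug discontinuation is not summarised separately. The size is at most 5.0 percentage points per such child if at least 20 are treated.

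It would be tempting to conclude that the reported figures do include such children and are overstated. The documents show only that the rule permits it; the number may be zero.

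The missing link between the End of Study reason and a particular AE is secondary. It could affect the system-organ-class and preferred-term table, the listing and the by-attack columns, but not normally the overall subject count.

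These conclusions assume that the three outputs use the definition in 4.2.2.1, as no other is given, and that a drug stop can be recorded for a child who stays in follow-up, as protocol 10.5 foresees. No sample size, power or error rate is affected.

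**What to change.** Replace the single definition in SAP 4.2.2.1 by two:

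- **TEAE leading to discontinuation of study drug:** the action-taken field of that AE record shows that the drug was discontinued.
- **TEAE leading to withdrawal from the study:** the End of Study reason is AE experience and the causal AE is identified, from the CRF if recorded there, otherwise at the Data Review Meeting.

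Show them as two rows in Table 14.3.1.1 and as separate panels or tables in place of the single Table 14.3.2.2. Listing 16.2.7.3 should state which of the two applies to each event.

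The SOP deviation form attached to the SAP says that the analysis is finalised, with version 3.1.0 taken as final. The change should therefore be described and justified in the clinical study report, the route that SAP 7.5 gives for changes after database lock. If the causal AE has to be identified at this stage, the report should say that the judgement was made after the analysis.

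The cost is one extra row and table, and a manual check of at most a few patients. The fields needed are already named in the SAP, except possibly the identity of the causal AE.
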